### Phase 1/Screening

Baseline Visit

Note: Study procedures and assessments during the baseline visit can be conducted over several visits until all inclusion/exclusion criteria are verified and patient is eligible to proceed with treatment (first study drug administration)

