### **b. Efficacy Analysis**

#### **i. Primary Endpoint**

The effect of GDC-0449 will be evaluated (at a significance level of 5% and controlling the false discovery rate) using Wilcoxon signed rank tests to compare the mean KCOT volume at baseline to those acquired at 6, 12, 24,36 and 48 months. These comparisons will also be accomplished using paired t-tests.

ii. Subject population for this analysis. As a primary intention to treat (ITT) analysis, we will analyze data from all randomized subjects who complete Phase 1. For these analyses, Phase 1 values will be substituted for missing observations. Should more than 20% of the data be missing at any observation interval, analysis of that interval will be abandoned. Deviations from this plan, for example, emergent interest in the analysis of the all-treated or protocol-compliant subjects, will be transparently pursued and reported.

iii. Treatment of missing data. Two secondary effectiveness analyses will either carry the last observation forward into missing cells, or use maximum likelihood estimates of those values. We expect the best estimate of efficacy is likely to lie within the limits set by these conservative (ITT) and liberal (LOCF, ML) treatments of missing data.

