#### **iv. Secondary Endpoints**

Secondary analysis will quantify the proportion of patients achieving minimal clinically significant changes in their tumors and comparing that to a theoretical expectation of 5% improvement with a Fisher exact test, and the effect of the *PTCH1* mutation on tumor volume reduction will be assessed with an independent samples t-test. These analyses will use the same population as the primary endpoint.

All analyses will be done using IBM SPSS Version 21.

v. Sample size determination. Twenty subjects will be recruited. Analysis of the primary endpoint is capable of detecting changes in tumor volume in the Wilcoxon tests of approximately 1.0 and .68 SD, assuming a 2-tailed type 1 error of 5% and power of 80% and then assuming either n=10 (separate analysis of the NBCSS-associated and sporadic cohorts) or n=20 (combined analysis of both cohorts), respectively (G\*Power, v3.1).

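### The primary intention-to-treat rule fills missing volumes with the baseline value, but the standard signed-rank test drops zero differences, so its p-value is an observed-case p-value at each interval

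*Combined protocol and SAP*

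**What the plan says.** Section 4.8 b.i sets the primary comparison, "using Wilcoxon signed rank tests to compare the mean KCOT volume at baseline to those acquired at 6, 12, 24,36 and 48 months", and adds a second test: "These comparisons will also be accomplished using paired t-tests".

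Section 4.8 b.ii applies the primary intention-to-treat analysis to everyone who completes Phase 1, with this rule for gaps: "For these analyses, Phase 1 values will be substituted for missing observations". Section 3.2 identifies that phase as "Phase 1/Screening", and its only visit is Baseline. Section 4.8 b.ii also sets a limit: "Should more than 20% of the data be missing at any observation interval, analysis of that interval will be abandoned".

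Section 4.8 b.iii adds last-observation-carried-forward and maximum-likelihood analyses as secondary, and expects the best estimate of efficacy to fall within "the limits set by these conservative (ITT) and liberal (LOCF, ML) treatments of missing data".

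Section 4.8 b.v gives detectable changes of about 1.0 SD for 10 pairs and 0.68 SD for 20 pairs, "assuming a 2-tailed type 1 error of 5% and power of 80" per cent. It makes no allowance for missing volumes. Section 4.8 b.iv names SPSS 21; no section says how zero differences are handled.

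**The concern.** The fill is meant to make dropouts count against the drug: a patient with no follow-up scan is treated as unchanged. A signed-rank test works on the signs and ranks of non-zero changes, and a change of exactly zero has no sign. The classical procedure sets such pairs aside and reduces the number of pairs. The rule therefore adds a patient and the test takes the same patient out.

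If the plan is followed to the letter, the report will show an observed-case p-value under an intention-to-treat label and describe it as conservative. The paired t-test beside it keeps the zeros, so one label would cover two tests with different effective samples. A reader would have no way to see this, because the plan does not ask for the number of pairs behind each p-value.

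**Working it through.** **Inputs.** From 4.8 b.i to b.v: signed-rank test, paired t-test, baseline fill, 20% limit per interval, two-sided alpha 0.05, power 80%, 10 or 20 pairs. Assumption: zeros are dropped, the classical rule, since the plan states none.

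**1. The fill and the signed-rank test.** For a filled patient, change = baseline - baseline = 0. With m observed changes and k filled ones, the test removes the k zeros and ranks the same m values, so the statistic, the number of ranked pairs and the p-value match those of the observed pairs. This is an identity and does not depend on why scans are missing. It was confirmed in 1,200 simulated datasets (1 or 2 of 10 filled, 2 or 4 of 20 filled): agreement in all 1,200. In a further 80,000 datasets the largest difference in p-value was 0.

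**2. What the fill does change.** Worked example with 8 observed changes and 2 filled:

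| Quantity | 8 observed | 8 observed + 2 filled |
|---|---|---|
| Mean change | -0.8375 | -0.8375 × 8/10 = -0.67 |
| Median change | -0.80 | -0.55 |
| Signed-rank statistic | 2 | 2 |
| Signed-rank p (normal approximation) | 0.0251 | 0.0251 |
| Paired t (df) | -3.103 (7) | -2.787 (9) |
| Paired t-test p | 0.017 | 0.021 |

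The t-test moves only slightly, for an algebraic reason. Let R = (Σx)²/Σx², which added zeros leave unchanged; then t² = R(n - 1)/(n - R). From t = 3.103 and n = 8, R = 4.633. At n = 10, t² = 4.633 × 9/(10 - 4.633) = 7.77, so |t| = 2.787, as in the table.

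**3. The plan's own detectable effects.** Method: noncentral t with the number of pairs multiplied by the asymptotic relative efficiency (ARE) of the signed-rank test under normality, 3/π. With N = 3n/π, df = N - 1 and noncentrality d√N, power is the probability of exceeding the upper 2.5% point of t.

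- n = 10: N = 9.55; at d = 1.0 the noncentrality is 3.09 and power 78%; 80% power needs 1.03 SD.
- n = 20: N = 19.10; at d = 0.68 the noncentrality is 2.97 and power 80%; 80% power needs 0.678 SD.

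These agree with the stated 1.0 and 0.68 SD, so the plan's figures are right for complete data.

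**4. The same method with missing volumes.** The 20% limit allows 2 of 10 or 4 of 20 to be missing, if it is applied to the sample being tested.

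| Pairs left | Detectable at 80% power | Power at the stated effect |
|---|---|---|
| 9 of 10 | 1.10 SD | 72% at 1.0 SD |
| 8 of 10 | 1.19 SD | 65% at 1.0 SD |
| 18 of 20 | 0.72 SD | 75.5% at 0.68 SD |
| 16 of 20 | 0.77 SD | 70% at 0.68 SD |

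**5. Source of the power loss.** Simulated power of the paired t-test with the fill against observed pairs only is 0.67 against 0.68 (2 of 10 filled, 1.0 SD) and 0.72 against 0.72 (4 of 20 filled, 0.68 SD). Keeping the filled patients recovers nothing, so the loss comes from the missing scans and not from the zero rule.

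**The case against.** The strongest reply is that the fill is not idle. The bracket in b.iii concerns the best estimate of efficacy, and the fill does pull the mean and median towards no change. The paired t-test keeps every filled patient. That stands: a reader might infer that the bracket is void or the fill pointless, and the documents do not support it. What fails is narrower, namely the conservative label on the signed-rank p-value.

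The damage is also bounded. The 20% limit caps the loss at 2 of 10 or 4 of 20 pairs, nothing changes if every scan is obtained, and 4.8 a already tabulates completers by time point. No inflation of the type I error has been shown. These points stand and lower the severity.

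The plan gives no zero rule, and a variant that ranks zeros would let the fill alter the p-value modestly. That is true, but such a variant would have to be specified, and it is not.

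Two further stronger readings should be resisted. One is that the primary test becomes a completers-only analysis: it does not, since a patient lost after month 6 still contributes at month 6. The other is that dropping zeros causes the loss of power, which step 5 rules out.

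**Conclusion.** The point holds as a should-fix. Under the standard treatment of zeros, the primary signed-rank p-value at each interval is the observed-case p-value whatever number of volumes is filled. It therefore lacks the intention-to-treat and conservative character that 4.8 b.ii and b.iii give it. The b.iii bracket can apply to the estimate only, and the two named tests run on different effective samples whenever a volume is missing.

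The missing allowance in b.v is a related but separate matter: at the 20% limit, detectable effects rise from 1.0 to about 1.19 SD and from 0.68 to about 0.77 SD, assuming normally distributed changes and the plan's apparent method. The documents give no expected rate of missing scans. Section 1.3 reports that 14 of 26 patients in a Gorlin-syndrome study stopped vismodegib for adverse events, but that is drug discontinuation elsewhere and cannot be read as a missing-scan rate here.

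**What to change.** 1. In 4.8 b.ii, call the signed-rank test an observed-case analysis at each interval, state that zero differences are dropped, and require the number of non-zero pairs beside each p-value. In b.iii, confine the conservative-to-liberal bracket to the estimate of change.
2. Rest the all-patient statement on analyses in which filled patients count: the mean change with its paired t-test, and the responder proportion already planned in 4.8 b.iv, with all treated patients in the denominator and missing counted as non-response. Section 4.8 b.iv gives no numerical threshold for response, so one has to be written in before the data are analysed.
3. In 4.8 b.v, say that 1.0 and 0.68 SD assume complete data and add the values at the 20% limit by the same method: about 1.19 SD for 8 pairs (power 65% at 1.0 SD) and 0.77 SD for 16 pairs (power 70% at 0.68 SD). Note that this loss comes from missing scans.

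The cost is a wording change with no new data and no new type of analysis. The stated detectable effects will look slightly less favourable.

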### 1.3.1 Malignancies with Mutation Driven Hh Pathway Signaling

#### 1.3.1.1 Basal Cell Carcinoma

##### Phase I Study SHH3925g - Safety and Pharmacokinetics Assessment

A Phase I, company-sponsored clinical trial (SHH3925g) assessed the safety and pharmacokinetics (PK) of vismodegib and responses of metastatic BCC (mBCC) or locally advanced BCC (aBCC) to the drug [10]. Thirty-three patients with mBCC or locally aBCC received oral vismodegib at one of three doses: 17 patients received 150 mg per day, 15 patients received 270 mg per day, and 1 patient received 540 mg per day (median duration of treatment was 9.8 months). Of the 33 patients, 18 had an objective response to vismodegib, according to assessment on imaging (7 patients), physical examination (10 patients), or both (1 patient). Of the patients who had a response (see Table 1), 2 had complete responses (CRs) and 16 had partial responses (PRs). The other 15 patients had either stable disease (11 patients) or progressive disease (4 patients). Eight Grade 3 adverse events (AEs) that were deemed to be possibly related to the study drug were reported in 6 patients (see Table 2), including fatigue (4 AEs), hyponatremia (2 AEs), muscle spasm (1 AE), and atrial fibrillation (1 AE). One patient withdrew from the study because of AEs.

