**Table 5: ERIVANCE® Safety Results at the 18-Month Update**

Number (%) of Patients with Adverse Events	Metastatic BCC (n = 33)	Locally Advanced BCC (n = 71)
All Patients with AEs	33 (100%)	71 (100%)
Grade 3-5 Adverse Event	14 (42.4%)	40 (56.4%)
Grade 5 Adverse Event §	1 (3%)	6 (8.5%)
Serious Adverse Events	8 (24.2%)	28 (39.4%)
Adverse Events Leading to Treatment Discontinuation	5 (15.2%)	16 (22.5%)

§ No new deaths on study since the primary data analysis. Fatal events included: Death of unknown cause (n=3), acute myocardial infarction (n=1), ischemic stroke (n=1), meningeal disorder (n=1), and hypovolemic shock (n=1). In all cases, clinically significant risk factors or comorbid conditions were present at baseline. Relationship between study drug and event is unknown.

BCC - basal cell carcinoma

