### Phase II BCNS Study (SHH4685s)

The anti-BCC efficacy of vismodegib was tested in a randomized, double-blinded, placebo-controlled, Investigator-sponsored trial in Gorlin syndrome (BCNS) patients with surgically eligible BCCs [13-15]. Forty-one patients were randomized 2:1 to receive oral vismodegib (n=26) or placebo (n=15). After a mean follow up of 8 months (range, 1 to 15 months), the per-patient rate of new surgically eligible BCCs (SEBs) was lower with vismodegib than with placebo (2 vs. 29 cases per group per year, p<0.001), as was the size (percent change from baseline in the sum of the longest diameter) of existing clinically significant BCCs (–65% vs. –11%, p=0.003). In some patients, all BCCs clinically regressed. No tumors progressed during treatment with vismodegib. Patients receiving vismodegib routinely had Grade 1 or 2 AEs of loss of taste, muscle cramps, hair loss, and weight loss. Overall, 54% of patients (14 of 26) receiving vismodegib discontinued drug treatment due to AEs. At 1 month, vismodegib use had reduced the Hh pathway's target-gene expression in BCC cells by 90% (p<0.001) and diminished tumor-cell proliferation, but apoptosis was not affected. No residual BCC was detectable in 83% of biopsy samples taken from sites of clinically regressed BCCs. At the second pre-specified interim analysis, a data safety and monitoring board concluded that the pre-determined threshold for a significant difference between the two groups had been reached (p<0.0113), and the treatment with placebo in this arm was terminated. AEs reported in ≥10% of patients are summarized in Table 9 See the Vismodegib Investigator's Brochure and the U.S. package insert for additional details on nonclinical and clinical studies on vismodegib.

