### **Phase II STEVIE (MO25616) Safety Study**

Study MO25616 is an ongoing Phase II open-label, single-arm, multicenter (ex-U.S.) study of vismodegib in patients with locally aBCC or mBCC who are otherwise without satisfactory treatment options. The primary objective is to assess the safety of vismodegib in patients with locally aBCC or mBCC. Secondary objectives are to assess the overall response (according to RECIST Version 1.1) in those patients with measurable disease as permitted by local regulatory requirement and to assess other efficacy parameters such as time to response, duration of response, PFS and overall survival (OS).

All patients receive 150 mg vismodegib orally (PO) daily (QD) until investigator-assessed PD, unmanageable toxicities, or withdrawal from study (investigator/patient request) or termination by the Sponsor).

As of 6 November 2013, a total of 1228 patients have been enrolled into the study. Results of an interim analysis, when a total of 501 patients could be followed for 1 year, are presented below.

As of the cutoff date of 6 November 2013, safety data were available for 500 patients (469 with locally aBCC and 31 with mBCC) with follow up information for at least 3 months after treatment. Overall, 492 of 500 safety-evaluable patients (98.4%) experienced at least one AE. The most frequently reported AEs, regardless of relationship to study drug, in descending order of frequency, were: muscle spasms (63.2%), alopecia (61.0%), dysgeusia (53.8%), weight decreased (32.4%), asthenia (28.2%), decreased appetite (25.4%), and ageusia (22.4%).

As of 6 November 2013, 210 of 500 safety-evaluable patients (42.0%) experienced Grade 3–5 treatment-emergent adverse events (TEAEs). Of 500 patients, 165 patients (33.0%) experienced a Grade 3 AE, 24 patients (4.8%) experienced a Grade 4 AE, and

21 patients (4.2%) experienced a Grade 5 AE. All of the Grade 5 AEs were considered by investigator to be unrelated to treatment with vismodegib except for cardio-respiratory arrest and myocardial infarction.

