Of the 500 patients, 107 (21.4%) experienced SAEs. The most common events were in the following system organ classes: infections and infestations, 30 patients (6.0%); neoplasms (benign, malignant, and unspecified, including cysts and polyps), 16 patients (3.2%); general disorders and administration site conditions, 12 patients (2.4%); nervous system disorders, 12 patients (2.4%); cardiac disorders, 11 patients (2.2%); injury, poisoning and procedural complications, 10 patients (2.0%); and metabolism and nutrition disorders, 10 patients (2.0%).

As of 6 November 2013, there have been 29 deaths among 500 safety-evaluable patients. The causes of death were PD in 4 patients, AE in 20 patients, and 5 patients with "other" as cause of death. Most patient deaths were considered unrelated to treatment with vismodegib. Two deaths (cardiopulmonary arrest and cardiac infarction) were assessed by the investigator as related to vismodegib; however, both patients had significant risk factors and comorbidities. Both events were considered by the investigator to be related because of the temporal relationship between the onset of the event and administration of vismodegib; therefore, an association could not be excluded.

As of 6 November 2013, 400 of 500 patients (80%) treated during Study MO25616 had discontinued study drug. Reasons for discontinuation of study drug included: AE (178 patients, 35.6%); progression of disease (70 patients, 14.0%); patient request (62 patients, 12.4%); death (10 patients, 2.8%); investigator request (14 patients, 2.8%); lost to follow-up (4 patients, 0.8%); and other (62 patients, 12.4%).

The majority of patients (98.2%) in Study MO25616 (STEVIE) experienced TEAEs. The most common (>20%) TEAEs included muscle spasm (63.2%), alopecia (61.0%), dysgeusia (53.8%), weight decreased (32.4%), asthenia (28.2%), decreased appetite (25.4%), and ageusia (22.4%). Twenty-four (4.8%) Grade 4 events and 21 (4.2%) Grade 5 events were reported. Two of the deaths were considered related to vismodegib treatment (cardio-respiratory arrest and myocardial infarction). There were 107 (21.4%) patients who reported SAEs. Common SAEs that were reported in  $\geq 1\%$  of patients were pneumonia (1.8%, n=9), general physical health deterioration (1.4%, n=7), and dehydration (1.0%, n=5).

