## **2. STUDY OBJECTIVES**

### **2.1 Primary Objectives**

The primary objectives of the study are:

- a. To evaluate the efficacy of GDC-0449 in reducing KCOT size (shrinkage) in NBCCS-associated KCOT and sporadic KCOT patients following 6 to 12 months of ingestion of 150 mg/day, up to 1 year of treatment and up to 2 years of post-treatment follow-up.
- b. To evaluate the safety of this dose of GDC-0449 in these patients.

*Tumor response (reduction in tumor volume and shrinkage) will be measured by volumetric CT scan.*

*Time Frame: Efficacy will be assessed at 1 year and 2 years after the study medication is stopped. Patients will undergo evaluation for 3 years (up to 1 year of treatment and up to 2 years of post-treatment follow-up). All patients will participate in the assessment of the safety and tolerability of the study drug. Safety monitoring will capture risks related to study participation and adverse events related to the study drug.*

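### The rule dropping any time point with more than 20% missing does not exempt month 12; loss is probable at the Gorlin trial's 54% discontinuation if patients who stop drug have no CT that counts

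*Combined protocol and SAP*

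**What the plan says.** Section 4.8 b.i compares tumour volume at baseline with volume at 6, 12, 24, 36 and 48 months, by Wilcoxon signed-rank test and also by paired t-test. Section 4.8 b.ii makes the primary analysis intention-to-treat with baseline values put in for missing ones, and then adds: "Should more than 20% of the data be missing at any observation interval, analysis of that interval will be abandoned". Section 4.8 b.iii adds last-observation-carried-forward (LOCF) and maximum-likelihood (ML) analyses, and expects the best estimate to lie between the conservative and the liberal treatments. Section 4.8 b.v uses all 20 patients, or all 10 per cohort, with no allowance for dropout.

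On patients who stop drug, the text points both ways:

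- **Towards leaving the study.** The Continuance Criteria in sections 4.4.3 and 4.4.4 release patients with progression or unacceptable toxicity. The risk text in section 4.4 discontinues from the study those who cannot resume after a three-month break.
- **Towards staying.** Section 4.5 lists the same events as reasons to stop therapy only. Section 4.6 words study discontinuation as optional. The first-dose text in section 4.4.2 speaks of stopping the drug. Section 2.1 says "Efficacy will be assessed at 1 year and 2 years after the study medication is stopped".
- **In between.** Appendix A schedules a volumetric CT at the discontinuation visit, but nothing says which interval it serves.

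Section 1.3.1.1 gives the background rates. For the Gorlin syndrome trial: "Overall, 54% of patients (14 of 26) receiving vismodegib discontinued drug treatment due to AEs", and "After a mean follow up of 8 months (range, 1 to 15 months". For the safety study: "Reasons for discontinuation of study drug included: AE (178 patients, 35.6" percent, at an interim analysis "when a total of 501 patients could be followed for 1 year". In the pivotal study's Table 5, the row "Adverse Events Leading to Treatment Discontinuation" shows 5 of 33 and 16 of 71. For Phase I: "One patient withdrew from the study because of AEs", out of 33.

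**The concern.** The drug's tolerability is the main foreseeable source of missing scans, and half of this trial's patients have the syndrome studied in the Gorlin trial. In a trial of 20 a 20% limit is tight, and the plan already has tools for missing data: baseline substitution at one end, LOCF and ML at the other. The rule switches the primary analysis off just when those tools are needed.

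At stake is the month-12 primary comparison. If the rule is read to cover LOCF and ML as well, the range between the conservative and liberal results goes too. A drug often stopped for toxicity could then have no end-of-treatment efficacy result. Restoring the interval after seeing its data would be a post hoc choice, even though section 4.8 b.ii permits openly reported deviations.

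**Working it through.** **The plan's own figure.** Section 4.8 b.v states detectable changes of about 1.0 SD (n=10) and 0.68 SD (n=20) at 80% power, two-sided 5%. Using a noncentral t with n multiplied by 3/π (an assumption about the software option) gives 1.026 and 0.678 SD. These agree with the stated values, and they use the full n.

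**Trigger.** 20% of 20 is 4, so more than 20% means at least 5 missing. 20% of 10 is 2, so it means at least 3. The plan does not say whether the data are counted in patients or tumours; I count patients, combined or per cohort.

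**Inputs.** Adverse-event discontinuation: Gorlin trial 14/26 = 53.8%; safety study 178/500 = 35.6%; pivotal study (5+16)/(33+71) = 21/104 = 20.2%; Phase I 1/33 = 3.0%. None is stated as a 12-month rate, so the accrual period m is varied as an assumption.

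**Formulas.** With constant hazard, the share stopped by month 12 is p12 = 1 − (1 − p)^(12/m). The chance of abandonment is P(X ≥ 5) for X ~ Bin(20, p12), or P(X ≥ 3) for X ~ Bin(10, p12). Patients are taken as independent. Example: Gorlin rate with m = 24 gives p12 = 1 − (12/26)^(1/2) = 0.321.

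**Month 12, no stopper with a CT that counts (n=20 / n=10):**

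| Rate | m = 12 | m = 18 | m = 24 |
|---|---|---|---|
| Gorlin 54% | 99.8% / 96.8% | 95.2% / 83.7% | 81.9% / 67.0% |
| Safety study 35.6% | 89.2% / 75.1% | 60.2% / 48.7% | 35.9% / 31.5% |
| Pivotal 20.2% | 37.9% / 32.8% | 13.6% / 15.4% | 5.5% / 8.2% |
| Phase I 1/33 | <0.1% / 0.3% | lower | lower |

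With m = 15, the longest follow-up in the Gorlin trial, that row is 98.5% / 91.2%.

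**Break-even.** Abandonment becomes more likely than not once true missingness exceeds 23.0% (n=20) or 25.9% (n=10). The pooled pivotal rate is below both, so at that rate no timing makes loss probable. The higher of its two cohorts, 16/71 = 22.5%, gives at most 48.1% at n=20.

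**Gorlin rate in the syndrome cohort only.** Adding Bin(10, 14/26) to Bin(10, 21/104) gives P(total ≥ 5) = 92.8%.

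**Some stoppers scanned (Gorlin rate, m = 12).** Half scanned: p = 0.269, giving 66.0% / 53.1%. Three-quarters scanned: p = 0.135, giving about 12% / 14%. To get below 50%, at least 1 − 0.230/0.538 = 57% (n=20) or 1 − 0.259/0.538 = 52% (n=10) must be scanned.

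**Sampling error.** The exact 95% interval for 14/26 is 33% to 73%. Its lower limit still gives 84.9% / 70.2%, with m = 12 and none scanned.

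**Month 6.** With m = 12, p6 = 1 − (1 − p)^(6/12), which is 0.321, 0.198 and 0.107. At n=20 abandonment is about 82% (Gorlin), 36% (safety study) and 5.5% (pivotal).

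**Zero differences (assumed data).** Nine completers shrinking by 10% to 50% in 5-point steps give signed-rank p = 0.0039, t-test p = 0.0002 and mean change −30%. Add 11 baseline-substituted patients (20 × 0.538 = 10.8 expected missing). The signed-rank p stays at 0.0039 because zeros are dropped, while the t-test p becomes 0.0029 and the mean change −13.5%.

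**The case against.** The strongest reply is that patients who stop drug may well be scanned. Section 4.5 separates stopping therapy from leaving the study, section 4.6 is permissive, and section 2.1 times follow-up from when medication stops. Section 4.8 a describes a time point falling between 6 and 12 months of treatment. That could be read as an end-of-treatment value, which the discontinuation CT would supply. This stands: it makes the risk conditional, and with three-quarters of stoppers scanned the risk is small even at 54%.

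A reader might infer that the trial's whole efficacy result is at risk. The documents do not support that. Month 6 is also a primary comparison and is probably lost only at the Gorlin rate. The rule sits in the intention-to-treat paragraph, and the text does not say whether it reaches LOCF and ML. Retention and adverse events are reported regardless.

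The 54% comes from 26 patients, half of this trial has sporadic tumours, and this protocol allows treatment breaks. That limits how far the rate carries over, although the mixed-cohort figure (92.8%) allows for the sporadic half. In the other direction, these rates omit stops for other reasons; discontinuation for any reason in the safety study was 80%.

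Declining to test a heavily incomplete time point can be defended as a safeguard. But the same caution is available by labelling the result, without withholding it.

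**Conclusion.** The concern holds in conditional form. The rule can remove the month-12 primary comparison. If patients who stop drug have no CT that counts for month 12, loss is probable at the Gorlin rate under every accrual period tried (12 to 24 months). It depends on timing at the safety-study rate, is possible but unlikely at the pivotal rate, and is negligible at the Phase I rate.

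Two stronger readings should be resisted. One is that loss is close to certain: that needs both the Gorlin rate and no usable scans, and the protocol settles neither. The other is that timing decides the matter at every lower rate: it does so only at the safety-study rate.

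The figures assume constant hazard, independent patients, a count in patients and adverse-event stops only. Confidence is medium, because scanning after drug stop is unresolved in the text. The point should be fixed, since the remedy is cheap and must be in place before data are seen.

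**What to change.** Delete the abandonment sentence in section 4.8 b.ii and replace it with wording such as:

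> Every scheduled CT time point will be analysed and reported with the number and reasons missing. Baseline-substitution, LOCF and ML results will be shown side by side. Time points with more than 20% missing will be labelled as uncertain.

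Add two statements:

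- The discontinuation-visit CT counts for a scheduled time point if it falls inside that visit's ±7-day window. Otherwise it enters LOCF and ML only.
- Baseline-substituted values are zero differences, which the standard signed-rank test drops. The paired t-test and mean change with baseline substitution are therefore the conservative result.

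The cost is analysis-plan wording, with no extra patients or scans. The downside is that estimates at heavily missing time points are less certain: the signed-rank result there reflects completers only, and the substituted t-test and mean change are pulled towards no change.

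Three related matters should be raised separately: how volumes after excision are handled, whether post-treatment CTs are timed from last dose or from baseline, and whether patients who stop drug stay on the CT schedule. The last needs a protocol amendment, which deleting the rule does not.

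### Missing volumes filled with maximum-likelihood estimates and, on the natural reading, tested as observed: this secondary analysis understates its standard errors, with single-visit type I error of about 9–10% rather than 5% at the plan's 20% missing-data ceiling

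*Combined protocol and SAP*

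**What the plan says.** All references are to the combined protocol and SAP, Section 4.8.b (Efficacy Analysis).

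- **Tests.** Item i describes the main comparison as "using Wilcoxon signed rank tests to compare the mean KCOT volume at baseline to those acquired at 6, 12, 24,36 and 48 months". Paired t-tests are added for the same comparisons. The error rule that item i sets for the evaluation is "at a significance level of 5% and controlling the false discovery rate". No other test of volume change over time is named.
- **Primary rule for missing volumes.** Item ii substitutes the Phase 1 (baseline) value.
- **Ceiling.** Item ii adds: "Should more than 20% of the data be missing at any observation interval, analysis of that interval will be abandoned".
- **Secondary rules.** Item iii gives two further analyses. One carries the last observation forward; the other will "use maximum likelihood estimates of those values". The values in question are the missing cells.
- **Role.** Item iii continues: "We expect the best estimate of efficacy is likely to lie within the limits set by these conservative (ITT) and liberal (LOCF, ML").

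Section 4.8 does not mention multiple imputation, added residual noise, a model fitted to the observed data alone, or a corrected standard error for filled data.

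**The concern.** The maximum-likelihood estimate of a missing cell is a point on a fitted line. It has no residual scatter of its own and hides the uncertainty in the fitted coefficients. If the completed column is passed to a paired t or signed-rank test, the test counts n patients when fewer were measured, and it sees less spread than real measurements would show. The estimate of mean change can be sound while its standard error and p-value are not.

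At stake is the reading of a supporting analysis. The plan sets the ML result beside the primary one as part of the range for efficacy. If its p-values are too small, it will seem to confirm an effect more often than it should. The trial has one arm, so there is no concurrent comparator against which to check a spurious change.

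**Working it through.** **Step 1. The plan's own figure.** Item v states detectable changes in the "Wilcoxon tests of approximately 1.0 and .68 SD" for n=10 and n=20, two-sided 5%, 80% power. Noncentral-t power with effective sample size n × 3/π gives 1.03 SD and 0.678 SD. The paired t gives 0.996 and 0.660. Simulated signed-rank power (20,000 runs) is 78.5% at 1.0 SD with n=10 and 80.2% at 0.68 SD with n=20. The stated figures reproduce, so these tests and sample sizes are the right base for the next steps.

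**Step 2. Inputs.** Two-sided alpha 0.05, n=10 per cohort and n=20 combined, and the 20% ceiling (2 of 10 or 4 of 20) come from Section 4.8.b. Assumed, because the documents are silent: normal data, values missing completely at random, between-visit correlation 0.5 to 0.95, and 5% or 10% missing as alternatives to the ceiling.

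**Step 3. Closed form for the simplest fill.** Let m of n changes be observed and fill the rest with the observed mean change. The mean and the sum of squares SS do not move. The reported SE is √[SS/(n(n−1))] where the observed pairs give √[SS/(m(m−1))]. So t is inflated by √[n(n−1)/(m(m−1))], and the true alpha is 2·P(T with m−1 df > t(0.975, n−1)/inflation).

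- n=20, m=16: √(380/240) = 1.258; 2.093/1.258 = 1.663; alpha = 0.117; SE ratio 0.795.
- n=10, m=8: √(90/56) = 1.268; 2.262/1.268 = 1.784; alpha = 0.118; SE ratio 0.789.
- n=20, m=18: √(380/306) = 1.114; alpha = 0.078; SE ratio 0.897.
- n=10, m=9: √(90/72) = 1.118; alpha = 0.078; SE ratio 0.894.

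**Step 4. Simulation with regression fills.** No true change. Missing volumes were predicted by ML regression from baseline alone, or from baseline plus one or two other visits, then treated as observed (paired t 40,000 runs, signed-rank 8,000). Ranges for type I error cover both tests and all correlations. The SE ratio is the paired t's mean reported SE divided by the true SD of the estimate.

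| Missing | Type I error, baseline only | SE ratio | Type I error, baseline plus 1–2 visits | SE ratio |
|---|---|---|---|---|
| 1 of 20 (5%) | 5.9–6.2% | 0.94–0.95 | 5.5–6.2% | 0.95–0.96 |
| 1 of 10 (10%) | 6.8–7.8% | 0.87–0.89 | 6.3–7.3% | 0.89–0.90 |
| 2 of 20 (10%) | 7.1–7.7% | 0.89–0.91 | 6.4–7.2% | 0.91–0.92 |
| 2 of 10 (20%) | 10.0–11.4% | 0.77–0.81 | 9.0–10.0% | 0.81–0.83 |
| 4 of 20 (20%) | 10.0–12.7% | 0.79–0.83 | 8.9–10.4% | 0.83–0.86 |

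The paired t on observed pairs only, in the same runs, gave 4.8–5.2%. A repeat simulation gave 8.8–9.7% with an SE 15–18% too small at 20% missing, and 6.4–7.2% at 10% missing.

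**Step 5. With false discovery rate control.** Benjamini-Hochberg applied to paired t-tests at four post-baseline visits, n=10, no change, correlation 0.5 to 0.8: the chance of any false positive was about 8% with 20% missing at both late visits. At correlation 0.5, with 10% missing at month 36, it was about 6%. Observed pairs gave about 5%.

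**The case against.** **The text does not say that fills are tested as observed.** This stands as a caution. Item iii gives one clause, with no algorithm, test or variance rule. The inference rests on the clause referring to the missing cells and on the plan naming only two tests for volume change. If a likelihood model on the observed data was meant, the wording still has to change to say so.

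**The analysis is secondary and labelled liberal.** This also stands, and it limits the weight of the point. The label describes how missing values are treated, however; it does not warn that the p-values are too small.

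**The bracketing sentence concerns an estimate, not its significance.** This is correct. With values missing completely at random, the filled estimate is essentially unbiased, so the bracket as a range of estimates is not damaged by this mechanism. The harm is confined to precision and p-values. The SE figures describe the paired t; for the signed-rank test the fault appears only in the p-value.

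**Single-visit rates ignore the planned multiplicity control.** Partly stands. Step 5 shows that the control reduces the excess without removing it at 20% missing.

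**The ceiling may not be approached.** No expected dropout is given. The background reports that 54% of vismodegib patients in the Gorlin syndrome trial, and 35.6% in the large safety study, stopped drug for adverse events. Those are treatment discontinuations, not missing scans. Even so, Section 4.6 allows discontinuation from the study for toxicity, and two lost patients put a cohort of 10 at the ceiling.

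**A mixed model is not automatically better at this size.** This stands and shapes the fix. In simulation at n=10, an unstructured ML fit with uncorrected Wald inference gave 11–13% (normal reference) or 7–9% (t with n−1 df).

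**Conclusion.** The fault is real, and it belongs to this secondary analysis. On the natural reading, single-visit type I error before false discovery rate control is about 9–10% at 20% missing (up to about 13% when the fill uses baseline alone), with an SE about 15–18% too small (up to about 23%). At 10% missing it is about 6–8%, and at 5% about 5.5–6.2%. All figures assume normal data, values missing completely at random and correlations of 0.5 to 0.95.

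A reader might infer more than the documents support:

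- **That the false-positive rate doubles in general.** It roughly doubles only at the ceiling. The 20% rule sits under the analysis population in item ii. If it did not bind the secondary analyses, the closed form gives about 17% at 30% missing, but nothing in the text says it does not bind.
- **That the primary result is compromised.** It is not; the primary analysis substitutes the Phase 1 value and uses no ML fill.
- **That the efficacy range is biased.** Under the assumed missingness it is not.

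The wording should be changed before analysis. The rule as written leads to wrong precision, and the correction is inexpensive.

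**What to change.** In Section 4.8.b.iii, replace the ML fill with a repeated-measures mixed model:

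- fitted by REML to the observed volumes at every CT visit in Appendix A (baseline, 6 and 12 months of treatment, 1 and 2 years after treatment);
- with fixed effects for visit, cohort and visit-by-cohort, so that cohort-specific changes can be estimated as item v contemplates;
- with a stated covariance structure and a fallback, since an unstructured matrix over five visits has 5 × 6/2 = 15 parameters for 20 patients;
- with small-sample degrees of freedom, such as Satterthwaite;
- with each visit's change and confidence interval taken from the model.

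If the signed-rank test is to be kept on filled data, use multiple imputation and state how the results are pooled. State also whether the 20% rule applies to the secondary analyses.

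The cost is SAP wording and one more standard model, with slightly wider intervals and no new data. The REML version with corrected degrees of freedom was not itself simulated here. A short simulation at n=20 before the SAP is finalised would confirm its error rate.
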